1.3. Overall Rationale for the Study

Although generally a self-limited disease, infection with influenza A can cause significant morbidity and mortality and may result in hospitalization, especially in certain patient populations such as those at the extremes of age.

Pimodivir is being developed for the treatment of patients who are hospitalized due to or at high risk of complications from influenza A, and who have the highest unmet medical need. As a therapeutic option intended for global use, studying pimodivir in combination with the SOC accounts for worldwide differences in the treatment of this population. In the instances where pimodivir is administered with a NAI SOC option, an additive effect of pimodivir over NAI administration alone will be explored in high-risk and hospitalized subjects. Further, the FLZ3001 study design is based on a recognition that local SOC approaches, particularly NAI, may have some benefit to patients even if used off label, as was noted above. Accordingly, the study design allows subjects to gain any potential benefits of the current SOC therapies, while also assessing the benefit of pimodivir.

The purpose of the current study is therefore to evaluate the additional benefit of pimodivir in combination with SOC treatment over placebo in combination with SOC treatment in adolescent (13 to 17 years), adult (18 to 65 years), and elderly (>65 to ≤85 years) hospitalized subjects with influenza A infection following a 5-day 600 mg bid therapy course.

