For the primary endpoint, the results from the proportional odds model will be used in the hypothesis testing. For the secondary endpoints time from start of study drug to hospital discharge, time from ICU admission to ICU discharge, time to return to daily activities, and time from start to end of mechanical ventilation, the results of the Gehan-Wilcoxon test will be used in the hypothesis testing. For incidence in post-baseline complications and rate of re-hospitalization the results of the logistic regression will be used.

Primary Endpoint

The primary efficacy analysis will be based on the ITT-i analysis set and consists of the analysis of the hospital recovery scale outcome on Day 6.

A proportional odds model will be used to analyze the hospital recovery scale, including at a minimum treatment and the stratification factors (baseline NEWS2, type of baseline SOC, and time since onset of influenza symptoms).

Model assumptions will be assessed by the score test for parallel slopes. In addition, each of 5 dichotomizations of the hospital recovery scale, ie,

- Not hospitalized, vs worse (ie, hospitalized)
- Non-ICU hospitalized without supplemental oxygen (or better), vs worse
- Non-ICU hospitalized with supplemental oxygen (or better), vs worse
- In the ICU without invasive mechanical ventilation (or better), vs worse
- Invasive mechanical ventilation (or better), vs worse (ie, died)

will be analyzed using a logistic regression model, including at a minimum treatment, hospital recovery scale category at baseline, and strata. The hospital recovery scale will also be analyzed using the Van Elteren test with strata defined by the stratification factors.

In case of more than 10% missing data on Day 6, multiple imputation will be employed as sensitivity analyses, under the missing-at-random (MAR) assumption and missing-not-at-random (NMAR) assumption. For the NMAR assumption, imputation under the MAR assumption will be applied, but with a structural shift in hospital recovery scale category of the imputed values, to introduce non-ignorable missing patterns:

- To reflect missingness patterns as a result of study discontinuation due to a dissatisfying treatment effect or safety issues in the placebo treatment group, the following shifts will be applied in the placebo treatment group only:
 - 1 category down, eg, from ‘1. Not hospitalized’ to ‘2. Non-ICU hospitalization, not requiring supplemental oxygen’

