1.4. Sample Size Justification

The study will enroll 600 subjects between the ages of 13 and 85 years, inclusive. Subjects will be randomized 1:1 to one of the treatment arms.

The sample size is based on the primary endpoint of the hospital recovery scale at Day 6. Based on the proportional odds model and assuming a benefit of approximately 38% reduction of the common odds ratio, a total sample size of 600 subjects (randomized 1:1) is required to obtain a power of 90% [11]. Inclusion of stratification factors would provide some improvement on the derived power.

In the sample size calculation it is assumed that the distribution of subjects treated with placebo in combination with SOC treatment will be as follows on Day 6:

- Not hospitalized: 30%
- Non-ICU hospitalization, not requiring supplemental oxygen: 30%
- Non-ICU hospitalization, requiring supplemental oxygen: 25%
- Admitted to the ICU, not requiring invasive mechanical ventilation: 5%
- Requiring invasive mechanical ventilation: 5%
- Death: 5%

This sample size is robust to mild to moderate changes in this distribution.

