5.1. Analysis Specifications

5.1.1. Level of Significance

The population used for the evaluation at the final analysis will depend on the outcome scenario of the interim analysis: i.e.; scenario 1: continue with the full study population or scenario 2: continue only with the subjects with an onset of symptoms less than 72 hours before first study drug intake. Tables/graphs/listings will account for the selected scenario.

As a confirmatory strategy, to account for multiplicity in the statistical evaluation of the most important efficacy endpoints, in either scenario, a combination of hierarchical testing and the Bonferroni-Holm testing procedure will be applied to control for the overall Type I error rate at the 5% level. The following endpoints are included in the confirmatory strategy:

1. Hospital recovery scale at Day 6, ie, primary endpoint
2. Incidence in post-baseline complications
3. Time to hospital discharge
4. Time from ICU admission to ICU discharge
5. Time to return to daily activities
6. Time from start of mechanical ventilation to end of mechanical ventilation
7. Rate of re-hospitalization

First, the primary endpoint will be tested for superiority of pimodivir in combination with SOC over placebo in combination with SOC at the 2-sided 5% significance level.

The confirmatory test procedure follows the Serial Gate Keeping strategy as outlined in Section 7 of the FDA's draft guidance on Multiple Endpoints to control the overall type I error at the 5% 2-sided level. The primary and six most important secondary endpoints (listed above) will be tested in the hierarchical order per the 5 steps outlined below. All alphas and p-values specified are 2-sided.

Step 1: Test the primary hypothesis ("Hospital recovery scale at Day 6")

- If the p-value is $\leq 5\%$, continue to Step 2.
- If the p-value is $> 5\%$, stop testing, and no claim will be made.

Step 2: Test first set of 2 secondary endpoints (“Incidence in post-baseline complications” and “Time from start of study drug to hospital discharge”). The Bonferroni-Holm procedure will be applied to control the type I error within Step 2.

- If the smallest of the 2 p-values is $\leq 2.5\%$ and the largest of the 2 p-values is $\leq 5\%$, continue to Step 3.

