5.2.3. Analysis Methods

A proportional odds model will be used as primary model to analyze the hospital recovery scale on Day 6, modeling the common odds ratio of improvement on the ordinal scale of active treatment versus placebo. The model will include treatment, hospital recovery scale category at baseline and the stratification factors (NEWS2 category at screening, type of baseline SOC, and time since onset of influenza symptoms). In a first step equal slopes (i.e. proportional odds) for the treatment effect only and unequal slopes for the other covariates, will be modeled. If this model does not fit a full

proportional odds model will be applied, i.e. implying proportional odds for all covariates in the model. The common odds ratio from the final model will be considered as the estimate of the treatment effect. The actual values of the stratification factors will be used for all models, not as randomized. The proportional odds model will be defined in such a way that a common odds ratio smaller than 1 indicates larger improvement in the pimodivir treatment group.

Graphical displays and tabulations will be provided showing the proportion of subjects per hospital recovery scale category and day. Also, shift tabulations will be provided of the baseline hospital recovery scale category versus the post-baseline hospital recovery scale category, per day.

The proportional odds assumption will be assessed by testing for parallel slopes for the treatment effect only.

In addition, each of 5 dichotomizations of the hospital recovery scale, ie,

- Not hospitalized, vs worse (ie, hospitalized)
- Non-ICU hospitalized without supplemental oxygen (or better), vs worse
- Non-ICU hospitalized with supplemental oxygen (or better), vs worse
- In the ICU without invasive mechanical ventilation (or better), vs worse
- Invasive mechanical ventilation (or better), vs worse (ie, died)

will be analyzed using a logistic regression model, including treatment, hospital recovery scale category at baseline and stratification factors.

The hospital recovery scale will also be analyzed using the Van Elteren test with strata defined by the stratification factors^[3, 6].

A table will be created showing the number (%) missing HRS values at day 6 overall and by reason: study discontinuation: due to COVID-19 and not due to COVID-19, discharged against medical advice prior to day 5 and subjects that have no confirmed influenza A.

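### The primary proportional odds model leaves out age and uses NEWS2 only as a two-level factor, giving up a small, uncertain amount of power that costs little to recover

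*SAP*

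**What the plan says.** SAP section 5.2.3 defines the primary model: "The model will include treatment, hospital recovery scale category at baseline and the stratification factors". The factors are NEWS2 category at screening, type of baseline SOC and time since symptom onset. NEWS2 has two levels, 4-5 and above 5 (SAP section 1.5). Age group reaches the primary endpoint only through the subgroup models (SAP sections 2.3 and 5.2.3).

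Protocol section 11.4 describes the same model as "including at a minimum treatment and the stratification factors", so further covariates are allowed. The SAP has already used that freedom once, by adding the baseline hospital recovery scale (HRS) category.

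Protocol section 3.2 says baseline severity and subject condition tend to be the strongest predictors of outcome, and treats NEWS2 as the best available measure of baseline status. Protocol section 1.3 says influenza A can cause serious illness and hospitalization "especially in certain patient populations such as those at the extremes of age". Age is an entry criterion (Protocol section 4.1, criterion 1). NEWS2 must be calculated before randomization because it decides both eligibility and stratum (first Time and Events Schedule, footnote n).

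**The concern.** Adjusting for a prognostic baseline variable raises power in a proportional odds model and leaves the test valid. The trial enrolls from 13 to 85 years and collects both variables by design, yet one is unused and the other is reduced to two levels.

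The NEWS2 cut is coarse by the SAP's own bands. Section 7.6.1 calls 1-4 low risk, 5-6 medium and 7 or more high. A cut between 5 and 6 splits the medium band and pools a score of 6 with every high-risk score.

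Baseline HRS may not fill the gap. Entry requires invasive ventilation or low oxygen saturation (Protocol section 4.1, criterion 5), so most subjects should start at category 3 or worse. Some planned covariates also drop out: type of SOC in the oseltamivir-subset analysis (SAP section 5), and time since onset if the final analysis is confined to subjects treated within 72 hours (SAP section 5.1.2).

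At stake is some of the power of the primary test, which gates every secondary claim.

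**Working it through.** **1. The plan's own figure.** Inputs from SAP sections 1.4 and 5.1.1:
- Test: "placebo in combination with SOC at the 2-sided 5% significance level".
- Size and power: "a total sample size of 600 subjects (randomized 1:1) is required to obtain a power of 90" percent.
- Effect: "assuming a benefit of approximately 38% reduction of the common odds ratio", read as OR 0.62.
- Allocation: "Subjects will be randomized 1:1 to one of the treatment arms".
- Placebo Day 6 distribution: 30/30/25/5/5/5%, beginning "Not hospitalized: 30" percent.

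OR 0.62 turns the placebo distribution into 40.9/29.9/19.4/3.4/3.3/3.2% on active treatment. With p̄ᵢ the mean of the two arms in category i, the Whitehead formula is

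N = 12(z₀.₉₇₅ + z₀.₉₀)² / [ln(OR)² (1 − Σp̄ᵢ³)]

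- Numerator: 12 × (1.960 + 1.2816)² = 126.1.
- Denominator: 0.2285 × 0.9174 = 0.2097.
- N = 601.4, against the stated 600. Power at N = 600 is 89.9%.
- Sensitivity: N = 563 at OR 0.61 and 643 at OR 0.63.

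The figure reproduces. It assumes no covariates.

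**2. The increment over the planned model.** The right comparator is the planned model, which already holds baseline HRS and the three strata. An unadjusted model is not the right one. Trials of 600 subjects were simulated, 1,500 per setting, with the conditional OR set so that the marginal OR is about 0.62.

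Assumed, because the documents are silent:
- Age: mean 60, SD 17.
- NEWS2: from 4 upward, mean 6.8, SD 2.3, 66% above 5.
- Baseline HRS: about 10% in category 4 or 5, with log OR 1.0 and 2.5 against category 3.
- Equal slopes for all covariates (the SAP's fallback model) and a single-stage test.

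| NEWS2 log OR per point | Age log OR per decade | Power, planned model | Power, + age + numeric NEWS2 | Information ratio | Subjects' worth at 600 |
|---|---|---|---|---|---|
| 0 | 0 | 92.3% | 92.1% | 1.00 | 0 |
| 0.1 | 0.1 | 93.5% | 94.1% | 1.01 | 7 |
| 0.1 | 0.2 | 93.1% | 93.9% | 1.03 | 20 |
| 0.2 | 0.2 | 94.2% | 95.6% | 1.06 | 38 |
| 0.3 | 0.3 | 94.1% | 96.9% | 1.14 | 85 |

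The information ratio is the squared ratio of mean z statistics. Subjects' worth is 600 × (ratio − 1), using unrounded ratios (for example 600 × 0.141 = 85). The Monte Carlo standard error of one power figure near 94% is √(0.94 × 0.06/1500) = 0.6 points, so the information ratio is the steadier guide.

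**3. What kind of gain it is.** In the 0.2/0.2 setting the standard error of the log OR rises slightly, from 0.1514 to 0.1528. The OR moves from 0.588 to 0.575, so the mean z goes from −3.505 to −3.616, and (3.616/3.505)² = 1.064. The gain is in power. The standard error does not shrink.

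**4. The combination test.** SAP section 5.1.2 requires two combination tests to succeed. Assume a homogeneous effect, 75% of subjects treated within 72 hours, an interim at 300 to 450 subjects and no increase in sample size. Single-stage power of 89.9%, 94.2% and 95.6% then becomes about 85%, 91% and 93%. The level falls, but the gain from the extra covariates stays about the same size.

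**The case against.** The strongest reply is that this is a preference about efficiency. The test is valid, the sample size is right, and the model already contains the outcome scale at baseline plus three prognostic strata. Zero gain lies inside the range. The top of the range needs strong effects of age and NEWS2 together, and the three middle settings give only 0.6 to 1.4 points. All of this stands.

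Several further points stand in part:
- **Age.** Protocol section 1.3 concerns influenza in general. It does not address Day 6 status in patients already hospitalized and hypoxic or ventilated. Its reference to both extremes of age also suggests a relation that a single linear term could miss.
- **NEWS2 completeness.** SAP section 5.1.4 falls back to the randomized category when the score cannot be recalculated, and a category supplies no number. The missing-value problem is real but solvable.
- **Ventilated subjects.** SAP section 7.6.1 replaces three components by fixed values worth 3 + 2 + 3 = 8 points, so numeric NEWS2 partly duplicates baseline HRS category 5.
- **Reach.** The confirmatory time-to-event tests are Gehan-Wilcoxon. If proportional odds fails for treatment, the formal p-value is Van Elteren (SAP section 5.1.1). The added covariates enter neither.
- **Estimand.** The common odds ratio becomes conditional on more covariates.

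A reader might infer from the 89.9% that the design has no power to spare. The documents do not support that. The figure ignores covariates, SAP section 1.4 expects the strata to add power, and SAP section 3.1 allows an increase to about 900 subjects. Under the assumptions above, the planned model has about 92 to 94% single-stage power. The two-test rule pulls the other way, but it applies with or without the extra terms.

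**Conclusion.** The point holds as a modest loss of efficiency. Age is missing, NEWS2 is cut to two levels, and the protocol leaves room for both. The gain over the planned model is about 0 to 3 points of power (information ratio 1.00 to 1.14, or 0 to 85 subjects' worth). It rests wholly on assumed prognostic effects and covariate distributions, equal slopes and a single-stage test. If neither variable is prognostic, including them costs almost nothing (92.3% to 92.1%).

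Two stronger readings should be set aside. A reader might infer that the primary analysis is biased or the trial undersized. It is not, since the test is valid and N = 600 reproduces. A reader might also infer that both variables can be added with no further rules because they are complete. That is true of age. For NEWS2 the SAP itself provides for incomplete recalculated scores.

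**What to change.** Amend SAP section 5.2.3 before the sponsor is unblinded:
- Add age as a continuous term with a proportional slope. If a non-monotone effect is expected, pre-specify a quadratic or spline term.
- Add the numeric screening NEWS2 score alongside the stratum, also with a proportional slope. State the rule for scores that cannot be fully recalculated, for example the score recorded at randomization or single imputation within the randomized category.
- Use the identical model for the pre- and post-interim p-values in section 5.1.2. The pre-interim group closed on 28 February 2020 (section 2.3) and the current SAP amendment is dated 1 July 2020, so blinded staff should make and document the change.
- Use the same covariates in the logistic models: the HRS dichotomizations, complications and re-hospitalization.

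If the sponsor keeps the present model, the SAP should record why age is left out and why the two-level NEWS2 was judged sufficient.

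The cost is SAP wording and programming, with no new data. The small downsides are the extra NEWS2 rule, the overlap with baseline HRS category 5, and an odds ratio conditional on more covariates.

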In case of more than 10% missing data on Day 6: multiple imputation will be employed as sensitivity analyses for the proportional odds model of the HRS (excluding the subgroup analyses), under the missing-at-random (MAR) assumption and missing-not-at-random (NMAR) assumption.

- If more than 5% of the patients have a missing HRS value due to COVID-19 (i.e.: discontinued due to COVID-19), the multiple imputation method will also be done separately on these subjects.
- If more than 5% of the patients have a missing HRS values unrelated to COVID-19, then also multiple imputation will be done separately in this group.

The Markov Chain Monte Carlo (MCMC) method will be used to create a number of multiple imputation datasets with monotone missingness in the clinical outcomes (baseline until Day 14). The number of imputation datasets will be the same as the percentage of missing data^[10]. For MAR assumptions, a monotone ordinal logistic regression imputation model will be used to complete the remaining missing clinical outcomes.

For the NMAR assumption, the imputed datasets obtained from the MAR assumption described above will be used, but with a structural shift in hospital recovery scale category on Day 6 of the imputed values, to introduce non-ignorable missing patterns:

- To reflect missingness patterns as a result of study discontinuation due to a dissatisfying treatment effect or safety issues in the placebo treatment group, the following shifts will be applied in the placebo treatment group only:
 - 1 category down, eg, from ‘1. Not hospitalized’ to ‘2. Non-ICU hospitalization, not requiring supplemental oxygen’
 - 2 categories down, eg, from ‘1. Not hospitalized’ to ‘3. Non-ICU hospitalization, requiring supplemental oxygen’
- To reflect missingness patterns as a result of study discontinuation due to a dissatisfying treatment effect or safety issues in the pimodivir treatment group, the following shifts will be applied in the pimodivir treatment group only:
 - 1 category down, eg, from ‘1. Not hospitalized’ to ‘2. Non-ICU hospitalization, not requiring supplemental oxygen’
 - 2 categories down, eg, from ‘1. Not hospitalized’ to ‘3. Non-ICU hospitalization, requiring supplemental oxygen’

In all cases, ‘6. Death’ will be the worst hospital recovery scale category after imputation and structural shift and ‘1 Not hospitalized’ will be the best hospital recovery category after imputation and structural shift.

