The models fitted using the multiple imputation datasets will be the same as the final model on the actual data. The results from the models on the multiple imputation datasets will be combined taking into account the between and within variation of the results.

The analyses on the primary endpoint will be repeated by subgroups for efficacy as defined in Section 2.3. The final model above will be repeated adding these subgroups (defined in Section 2.3) as an additional covariate and interaction with treatment. Per subgroup the common odds ratio and the odds ratios calculated for the dichotomizations will be derived from these models. In addition, for each category in a subgroup, the Van Elteren test with strata defined by the stratification factors will be repeated.

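### Setting the number of imputations equal to the percentage missing leaves enough random error for a borderline Day 6 sensitivity p-value to cross 5% on a change of seed

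*SAP*

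**What the plan says.** SAP 5.2.3 makes multiple imputation (MI) conditional: "In case of more than 10% missing data on Day 6: multiple imputation will be employed as sensitivity analyses". Two further runs, each confined to one cause of missingness, are listed beneath that sentence: "If more than 5% of the patients have a missing HRS value due to COVID-19", and "If more than 5% of the patients have a missing HRS values unrelated to COVID-19". The number of datasets follows one rule, with a methods reference attached: "The number of imputation datasets will be the same as the percentage of missing data".

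The imputation model draws on the daily scale scores from baseline through Day 14. The missing-not-at-random (NMAR) analyses take the missing-at-random (MAR) datasets and worsen the imputed Day 6 scores by one or two categories, in one arm at a time, giving four shift scenarios. Results are "combined taking into account the between and within variation of the results".

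The MI text sets no minimum number of imputations, no seed and no check of Monte Carlo error. It also does not say whether the percentage in the rule is the overall one or, for the cause-specific runs, the percentage missing for that cause.

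**The concern.** MI is random, so its p-value depends on the seed unless there are enough imputations. A rule that ties their number to the percentage missing gives few imputations exactly when an analysis has only just been triggered. It also does not buy more precision as missingness rises, because the added imputations only keep pace with the added uncertainty.

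SAP 5.2.2 presents MI as the sensitivity analysis for missing data. Nothing else in 5.2.3 varies the missing-data assumption: the Van Elteren test and the dichotomized models address model form, and the table of missing values by reason is descriptive. If a MAR or shifted result lies near 5%, whether it is reported as agreeing with the primary result could depend on the seed.

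**Working it through.** **Inputs from the documents**
- m = percentage missing; MI triggers at >10% (all causes) and >5% (each cause): SAP 5.2.3.
- Two-sided 5% level: SAP 5.1.1.
- 600 subjects, 1:1, 90% power, "assuming a benefit of approximately 38% reduction of the common odds ratio", placebo Day 6 distribution 30/30/25/5/5/5%: SAP 1.4.

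**Input not in the documents.** FMI depends on how well the other days predict Day 6. I take a range from about 0.02–0.04 (strongly informative other days) up to the missing fraction (uninformative).

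**Step 1: reproduce the plan's own figure.** Whitehead's formula is N = 12(z₀.₉₇₅ + z₀.₉₀)² / [(ln OR)²(1 − Σp̄³)].
- With OR = 0.62, (ln OR)² = 0.2285.
- The mean category proportions are 0.354, 0.299, 0.222, 0.042, 0.041 and 0.041, so Σp̄³ = 0.0825.
- N = 12 × 10.507 / (0.2285 × 0.9175) = 602 after rounding up. Power at 600 is 89.9%.

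This agrees with the SAP, so the same setting was used for the simulation in Step 4.

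**Step 2: Monte Carlo error.** The pooled estimate has between-imputation noise B/m. With total variance T and FMI ≈ B/T, the SD of z over seeds is sqrt(FMI/m). For a two-sided p near 0.05, SD(p) ≈ 2φ(1.96) × SD(z) = 0.117 × SD(z).

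| FMI | m | SD(z) | SD(p) at 0.05 | Chance p>0.05 if converged p = 0.045 | if 0.04 |
|---|---|---|---|---|---|
| 0.11 | 11 | 0.100 | 0.012 | 33% | 17% |
| 0.06 | 6 | 0.100 | 0.012 | 33% | 17% |
| 0.20 | 20 | 0.100 | 0.012 | 33% | 17% |
| 0.06 | 11 | 0.074 | 0.009 | 27% | 10% |
| 0.04 | 11 | 0.060 | 0.007 | 23% | 6% |
| 0.02 | 6 | 0.058 | 0.007 | 22% | 5% |
| 0.02 | 11 | 0.043 | 0.005 | 15% | 1% |

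The converged p is the value with a very large number of imputations. Each crossing chance is Φ((1.960 − z)/SD(z)), with z = 2.005 for p = 0.045 and z = 2.054 for p = 0.04. The first three rows show that when FMI equals the missing fraction f and m = 100f, SD(z) = sqrt(f/100f) = 0.10 at any level of missingness.

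**Step 3: what that means at the threshold.** With SD(z) = 0.10 and a converged p of 0.05, 95% of seeds give z from 1.76 to 2.16, that is p from 0.031 to 0.078. With FMI 0.04 and m = 11, a result at z = 2.0 spans, at ±2 SD, z from 1.88 to 2.12, or p from 0.034 to 0.060.

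**Step 4: simulation check.** The simulation used 600 subjects, the SAP placebo distribution, ordinal-logistic imputation and pooling by Rubin's rules. There were three fixed datasets per setting, each with 4,000 re-draws of m imputations from 500.
- 11% missing, m = 11, no help from other days (FMI 0.10–0.11): converged p of 0.036, 0.043 and 0.048 exceeded 5% in 15%, 31% and 47% of runs; SD(p) 0.011–0.012.
- 6% missing, m = 6, no help (FMI 0.06–0.07): converged p of 0.032, 0.043 and 0.048 exceeded 5% in 5%, 33% and 46%; SD(p) 0.009–0.013.
- With a strongly correlated Day 5 score: FMI about 0.04 at 11% missing and 0.02 at 6%; SD(p) 0.005–0.007. A converged p of 0.047 crossed in 37% of runs (m = 11) and 0.042 in 12% (m = 6). Values of 0.033–0.038 crossed in 0.1–3%.

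**Step 5: effect of 100 imputations.** SD(z) is sqrt(0.11/100) = 0.033, sqrt(0.06/100) = 0.024 and sqrt(0.04/100) = 0.020, or 0.014 at FMI 0.02. At FMI 0.11, the chance of crossing falls from 33% to 9% for a converged p of 0.045, and from 17% to 0.2% for 0.04. A result at z = 2.0 still spans, at ±2 × 0.033, p from about 0.039 to 0.053.

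These figures treat the sensitivity result as a single pooled z. The formal test combines pre- and post-interim p-values (SAP 5.1.2), and 5.2.3 does not say whether the MI results would be combined in that way.

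**The case against.** Four counter-arguments deserve weight.

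1. **Nothing confirmatory depends on MI.** A reader might infer that the primary conclusion could flip with the seed. The documents do not support that. Superiority is tested over "placebo in combination with SOC at the 2-sided 5% significance level" using the proportional odds model, or the Van Elteren test if proportionality fails for treatment (SAP 5.1.1 and 5.2.2). No claim or threshold is attached to an MI p-value, and reading one as significant or not is an inference about how it would be used. This stands, and it makes the point minor.

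2. **Six to eleven is not the number of imputations.** Those are values at the triggers, and m would be 20 at 20% missing. The value 6 needs the cause-specific percentage to set m. If the >5% runs are nested under the >10% condition and the overall percentage governs, every run has about 10 to 11 or more. This also stands, but the error need not shrink as m grows, because FMI can grow with it.

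3. **Other days inform Day 6.** An error fixed at 0.10 whatever the missingness would hold only if FMI equalled the missing fraction. Strong prediction from other days roughly halves it, so the result must be given as a range. Values close to 5% still cross.

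4. **The rule is referenced, and 100 is not in the documents.** Both are true. The reference was not available to check, but a citation does not alter the arithmetic. The figure of 100 is a choice of precision.

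A reader might also see a flaw in the shift analyses reusing the MAR datasets. That is not one: common draws reduce the noise in the MAR-to-NMAR comparison, which is what the shifts are meant to show.

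**Conclusion.** The point holds as a minor matter of precision. Under the SAP rule the SD of z over seeds is about 0.06 to 0.10 in most of the cases considered, and about 0.04 in the most favourable. The SD of a p-value near 0.05 is about 0.005 to 0.012. A MAR or NMAR result within roughly 0.01 of 5% could be reported on either side of it by seed alone; with a converged p of 0.03 the chance is at most about 2% by formula (5% in the simulated 6%-missing case with a converged p of 0.032).

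This rests on the assumed FMI range, on MI being triggered at all, and, for m near 6, on the cause-specific percentage setting m. The documents support no stronger conclusion: the confirmatory test, the alpha allocation and the sample size do not change.

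**What to change.** In SAP 5.2.3, replace the sentence on the number of datasets with a fixed number of at least 100 imputations and a pre-specified seed for every MAR and NMAR run, including the COVID-19 and non-COVID-19 runs. Report the Monte Carlo error of each pooled estimate and p-value beside the result. A fixed number also removes the question of which percentage sets m. The shift analyses can go on using the MAR datasets.

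No finite number removes the seed's influence when the converged p is very close to 5%, which is why the Monte Carlo error should be reported. The cost is one SAP sentence and slightly longer run time, with no effect on trial conduct.
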